## 2. LIST OF ABBREVIATIONS AND DEFINITIONS

AE	Adverse Event
ALT	Alanine Aminotransferase
ANOVA	Analysis Of Variance
APTS	All Patients Treated Set
ARR	Annualized Relapse Rate
AST	Aspartate Aminotransferase
BUN	Blood Urea Nitrogen
CRF	Case Report Form
CRO	Contract Research Organization
DMT	Disease Modifying Treatments
EDC	Electronic Data Capture
EDSS	Expanded Disability Status Scale
ET	Early Termination
FPI	First Patient In
FSS	Fatigue Severity Scale
GCP	Good Clinical Practice
GGT	Gamma-Glutamyl-Transferase
ICF	Informed Consent Form
ICH	International Conference on Harmonisation
IFN	Interferon
IWRS	Interactive Web Response System
LPI	Last Patient In
LPLV	Last Patient Last Visit
MCH	Mean Cell Hemoglobin
MCHC	Mean Corpuscular Haemoglobin Concentration
MCV	Mean Corpuscular Volume
MSTCQ	Adapted Sclerosis Treatment Concerns Questionnaire
MusiQoL	Multiple Sclerosis International Quality of Life questionnaire
PHI	Protected Health Information
RBC	Red Blood Cell
RRMS	Relapsing-Remitting Multiple Sclerosis
SAE	Serious Adverse Event
SC	Subcutaneous
SD	Standard deviation
SMPC	Summary of Product Characteristics
SUSAR	Suspected Unexpected Serious Adverse Reactions
TSQM	Treatment Satisfaction Questionnaire to Medication
WBC	White Blood Cell

CONFIDENTIAL

The information contained herein may not be used, disclosed, or published without the written consent of Biogen Italia

### 3. SYNOPSIS

This is a brief summary. For details refer to the body of the protocol.

Protocol Number:	BIIT0215
Protocol Title:	Multicenter interventional Phase IV study for the assessment of the effects on patient's satisfaction of Plegridy (pre-filled pen) in subjects with relapsing-remitting multiple sclerosis unsatisfied with other injectable subcutaneous Interferons ( PLATINUM )
Version Number:	5.0 23 July 2015
Name of Study Treatment:	Plegridy - Peginterferon beta-1a (Peg-IFN beta-1a)
Study Indication:	Relapsing-Remitting Multiple Sclerosis (RRMS)
Phase of Development:	4
Rationale for the Study:	
Satisfaction with treatment has recently been included among health outcomes research variables, due to its value for health care evaluation as well as for its relevant implications in clinical practice. In fact, there is evidence that patients feeling satisfied with their treatment show better compliance with prescriptions and play an active role in their own care.
 
The treatment based on Peg-IFN 125 µg - administered subcutaneously (SC) every 2 weeks - is effective in RRMS, it requires less-frequent injections and it is associated with a positive safety profile, comparable with that of the other currently approved first-line injectable therapies. The reduced frequency of administration might render pegylated interferon beta more tolerable, improving its convenience and providing an alternative to the established dosing regimens.
 
This phase IV, interventional, multicenter study aims at evaluating whether Peg-IFN 125 µg administered subcutaneously (SC) every 2 weeks improves patients' satisfaction and adherence rate in RRMS subjects unsatisfied with other injectable subcutaneous Interferons.
 
In addition, the study may provide data on Peg- IFN effects

CONFIDENTIAL

The information contained herein may not be used, disclosed, or published without the written consent of  
Biogen Italia

on health-related quality of life and other relevant patients' reported outcomes.

## Study Objectives and Endpoints:

### Objectives

#### Primary:

The primary objective of the study is to investigate whether Peg-IFN beta-1a improves patients' satisfaction in RRMS subjects unsatisfied with other injectable subcutaneous Interferons, as measured by the Abbreviated Treatment Satisfaction Questionnaire to Medication (TSQM-9), across a 12-weeks observation period.

#### Secondary:

The secondary objectives of this study consist in the evaluation, in this study population, of the following parameters:

- effects of Peg-IFN beta-1a treatment on patients' satisfaction at 24 weeks;
- effects of Peg-IFN beta-1a treatment on short-term patients' adherence;
- impact of Peg-IFN beta-1a treatment on patient-reported health-related quality of life;
- effects of Peg-IFN beta-1a treatment on patients' fatigue;
- impact of Peg-IFN beta-1a treatment on patients' injection-system satisfaction;
- effects of Peg-IFN beta-1a on disease activity and physical disability;
- relationship between patients' satisfaction and adherence;
- relationship between patients' satisfaction and social-demographic factors (age, sex, employment working, level of education, etc) and clinical characteristics (ARR, disability, etc.)

### Endpoints

#### Primary:

Changes from baseline in the score of convenience satisfaction domain of TSQM-9 at 12 weeks.

CONFIDENTIAL

The information contained herein may not be used, disclosed, or published without the written consent of Biogen Italia

Secondary:

- Changes from baseline in the score of all domains of TSQM-9 at 24 weeks;
- Changes from baseline in patient adherence to treatment at 12 and 24 weeks, as evaluated by the adherence questionnaire;
- Changes from baseline in the score of FSS (Fatigue Status Scale) at weeks 12 and 24;
- Changes from baseline in the score of Adapted Sclerosis Treatment Concerns Questionnaire (MSTCQ) at weeks 12 and 24;
- Changes from baseline in the score of Multiple Sclerosis International Quality of Life questionnaire (MusiQoL) at weeks 12 and 24;
- Changes from baseline in clinical measures (ARR, percentage of relapse-free patients, EDSS) measures at week 24.
- Incidence and severity of adverse events occurred during the study (including local tolerance to treatment at the injection site).
- Abnormalities in laboratory values.

Study Design:

This is a 6 month, open-label, single-arm, interventional, multicentric study based on patient self-administered questionnaires (as described in Methods), aimed at evaluating subject-reported effects on satisfaction with treatment of Peg-IFN beta-1a in subjects unsatisfied with other injectable, subcutaneous Interferons.

Evaluations will be performed at baseline (T0), week 12 (T1) and week 24 (T2) of treatment respectively.

Centres involved: 35, located all over Italy.

Number of visits: 3

Subjects attending the recruiting centers, meeting the eligibility criteria and signing the written Informed Consent Form (ICF) will be enrolled in the study.

Each enrolled patient will perform baseline visit (T0), visit T1(12 weeks after the start of Peg-IFN treatment) and visit T2 (24 weeks after the start of Peg-IFN treatment).

CONFIDENTIAL

The information contained herein may not be used, disclosed, or published without the written consent of Biogen Italia

Early Termination (ET) visit will be foreseen for possible study discontinuations required by either patient's or investigator's decision.

At the baseline visit (T0), following the administration and obtainment of the signed ICF, patients will undergo the eligibility assessment according to the protocol inclusion/exclusion criteria, and the registration of socio-demographic and medical history data .

The following activities will be performed at all the study timepoints (T0, T1 and T2):

1. registration of concomitant diseases;
2. registration of concomitant medications;
3. evaluation of clinical and neurological (EDSS) conditions, adherence to treatment, occurrence of any adverse events and/or laboratory parameters abnormalities.

Moreover, at each visit patients will be administered the study questionnaires in order to evaluate:

1. Patients' satisfaction (TSMQ-9 test);
2. Patients' injection-system satisfaction (adapted MSTCQ test);
3. Patients's quality of life (MusiQoL test);
4. Patients' fatigue (FSS test).

Questionnaires will be completed electronically, by means of an i-PAD that provided by the Sponsor to the centers involved in the study. Patients unable to complete the electronic format will be supplied with paper hard copies of the questionnaires, in order to ensure proper data collection.

CONFIDENTIAL

The information contained herein may not be used, disclosed, or published without the written consent of  
Biogen Italia

**Rationale for Dose and  
Schedule Selection:**

Peg-IFN beta-1a (Plegridy®) is a solution for subcutaneous injection in pre-filled pen and will be administered fortnightly at a dose of 125 mcg.

The treatment involves a dose titration phase followed by a maintenance phase, according to the following scheme:

Titration phase:

Plegridy® 63 micrograms on day 1 of treatment

Plegridy® 94 micrograms on day 14, i.e. two weeks after the first dose.

Maintenance phase:

Plegridy® 125 micrograms on day 28 after the first dose and then every two weeks.

Patients will thus start treatment with 63 micrograms at dose 1, increasing to 94 micrograms at dose 2, reaching the full dose of 125 micrograms by dose 3 and continuing with the full dose (125 micrograms) every 2 weeks thereafter.

The total duration of treatment will be of 24 weeks (titration phase and maintenance phase).

Every effort should be made to administer Plegridy® at the same time and at the same day of the week.

**Study Location:**

The trial is planned to be performed at 35 sites in Italy, with competitive enrolment.

**Number of Planned Subjects:**

Approximately 275 subjects will be treated in the study.

**Study Population:**

This study will be conducted in subjects with Relapsing-Remitting Multiple Sclerosis (RRMS) as per 2010 McDonald criteria, with EDSS between 0.0 and 5.0 and unsatisfied with the current injectable subcutaneous Interferons.

Detailed criteria are described in the protocol.

**Treatment Groups:**

Single arm study: All subjects enrolled after the first period (4 weeks) of dose titration will be treated with Peg IFN beta-1a 125 mcg (every 2 weeks) for a total period of 24 weeks.

**CONFIDENTIAL**

The information contained herein may not be used, disclosed, or published without the written consent of Biogen Italia

**Visit Schedule:** Baseline T0: start of treatment with Peg IFN beta-1a.  
T1: 12 weeks of treatment with Peg IFN beta-1a.  
T2: 24 weeks of treatment with Peg IFN beta-1a.  
ET (Early Termination): in case of early termination of the study.  
See flow chart.

**Planned duration of Treatment and Follow-up:** First Subject In (FPI): Sept/2015  
Last Subject In (LPI): Sept/2016  
Last Subject Last Visit (LPLV): March 2017

**Criteria for Evaluation:** *Inclusion criteria*  
18 ≤ Age ≤ 65 years  
RRMS as per 2010 McDonald criteria  
Baseline EDSS between 0.0 and 5.0  
Treatment with injectable subcutaneous Interferons with score < 58 in the "convenience satisfaction" domain of TSQM-9  
Signed informed consent  
Period of stability from last relapse of at least 30 days before the baseline visit.  
Treatment with intravenous corticosteroids completed at least 30 days before the baseline visit (assumption of oral cortisone allowed as long as within 4 mg per day for no longer than 3 days).

*Exclusion criteria*

Pregnancy or breast-feeding  
Depression or other psychiatric disorders  
Unwillingness or inability to comply with the protocol requirements  
Any contra-indications to treatment with Peg-IFN-beta 1a according to the Summary of Product Characteristics

**Efficacy:** Being this is a health outcomes research study, in the present protocol the term *efficacy* is referred to the

CONFIDENTIAL

The information contained herein may not be used, disclosed, or published without the written consent of Biogen Italia

assessment of the following patients' reported parameters, corresponding to the primary and secondary objectives of the study, and to the measurement of the related endpoints:

- overall treatment satisfaction,
- injection system satisfaction,
- adherence to treatment,
- health-related quality of life,
- fatigue.

*Safety:* Treatment tolerability will be assessed and all adverse events occurring during the study and changes in laboratory parameters will be collected. Also pregnancy and episodes of overdose will be collected.

*Additional:* Not applicable.

*Statistical Methods:* Descriptive statistics of T0, T1 and T2 values, of all the collected variables as well as the relevant changes from baseline will be presented as mean, and standard deviations, along with median values and ranges. The primary endpoint (change of TSQM-9 convenience domain at week 12) will be analyzed by a repeated measures analysis of variance adjusted for baseline factors (age, sex, disease duration, previous treatment duration, EDSS). The same technique will be adopted also for the analysis of the other endpoints. Correlations between variables will be assessed through the Spearman rank correlation coefficient.

*Interim Analysis:* No interim analysis will be performed.

*Sample Size Determination:* Data for estimating the sample size were derived from studies reporting the distribution (mean value and standard deviation) of the TSQM-9 in MS patients treated with IFN (9). Assuming an average value of the overall convenience domain at baseline of 55 (SD=16), 250 subjects allow a power of 90% to detect a change of 3 points on the overall convenience domain (from 55 to 58) under the conservative hypothesis of a SD=16 for the difference between baseline and week 12.

However, by assuming a drop-out rate up to 10% during the study, we consider it appropriate to enrol a total of 275 patients.

CONFIDENTIAL

The information contained herein may not be used, disclosed, or published without the written consent of Biogen Italia

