### *Clinical Experience with Peg-IFN*

The efficacy and safety of Peg-IFN 125  $\mu$ g was assessed from the placebo-controlled first year of a 2 year randomised, double-blind, clinical study in patients with relapsing remitting multiple sclerosis (the ADVANCE study). 1512 patients were randomised to and dosed with 125 micrograms Peg-IFN 125  $\mu$ g injected subcutaneously every 2 (n=512) or 4 (n=500) weeks versus placebo (n=500)(11).

The primary endpoint was the annualized relapse rate (ARR) over 1 year. The study design and patient demographics are presented in the Table below.

No data are available from clinical efficacy/safety studies directly comparing pegylated with non-pegylated interferon beta-1a, or from patients switching between non-pegylated and pegylated interferon.

Study design	
Disease history	Patients with RRMS, with at least 2 relapses within the prior 3 years, and 1 relapse in the prior year, with an EDSS score of $\leq$ 5.0
Follow-up	1 year
Study population	83% treatment-naïve patients 47% $\geq$ 2 relapses in prior year 38% at least 1 Gd+ lesion at baseline 92% $\geq$ 9 T2 lesions baseline 16% EDSS $\geq$ 4 17% previously treated
Baseline characteristics	
Mean age (years)	37
Mean/Median disease duration (years)	3.6/2.0
Mean number of relapses within the past 3 years	2.5
Mean EDSS score at baseline	2.5
EDSS: Expanded Disability Status Scale Gd+: Gadolinium-enhancing	

Peg-IFN 125 µg every 2 weeks significantly reduced the annualized relapse rate (ARR) by 36% compared to placebo (p=0.0007) at one year (see Table below) with consistent reductions of the ARR noted in subgroups defined by demographic and baseline disease characteristics. Peg-IFN 125 µg also significantly reduced the risk of relapse by 39% (p=0.0003), the risk of sustained disability progression confirmed at 12 weeks by 38% (p=0.0383) and at 24 weeks (post-hoc analysis) by 54% (p=0.0069), the number of new or newly enlarging T2 lesions by 67% (p<0.0001), the number of Gd-enhancing lesions by 86% (p<0.0001) and the number of T1 hypointense lesions compared to placebo by 53% (p<0.0001). A treatment effect was observed as early as 6 months, with Peg-IFN 125 µg every 2 weeks demonstrating a 61% reduction (p<0.0001) in new or newly enlarging T2 lesions as compared with placebo. Across relapse and MRI endpoints Peg-IFN 125 µg every two weeks showed a numerically greater treatment effect over the Peg-IFN 125 µg every four weeks dosing regimen at year 1.

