### **16.3.2. General Methods of Analysis**

The primary and secondary endpoints will be evaluated using a repeated measures ANOVA. The repeated measures ANOVA is used to compare group means on a dependent variable across repeated measurements of time. This statistical method is used for making simultaneous comparisons between two or more means of two or more related, not independent, groups.

However, in addition, it could be useful to apply a general linear mixed model that models for group means as fixed effects while simultaneously modeling for individual subject variables as random effects (12).

This kind of model is a subject-specific model and is a choice for analysing longitudinal data.

Unlike the repeated measures ANOVA, which requires a complete balanced array of data, the mixed model can accommodate a dataset with a large portion missing. Although the repeated measures ANOVA requires a fixed time schedule among all individual units, the mixed model can accommodate flexible time schedules. Furthermore, rather than treating time as a categorical variable, as in the repeated measures ANOVA, the mixed model is capable of treating time as either a continuous variable or a categorical variable or both.

Spearman's correlation coefficient measures the strength of association between two ranked variables.

Differences will be considered statistically significant if the p-value will be less or equal to a type I error =0.05 (two-sided test).

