### **16.5. Sample Size Considerations**

Data for estimating the sample size were derived from studies reporting the distribution (mean value and standard deviation) of the TSQM-9 in MS patients treated with IFN (9). Assuming an average value of the overall convenience domain at baseline of 55 (SD=16) (9), with 250 subjects we have a power of 90% to detect a change of 3 points on the overall convenience domain (from 55 to 58) under the conservative hypothesis of a SD=16 (9) for the difference between baseline and week 12. However, by assuming a drop-out rate up to 10% during the study, we consider it appropriate to enrol a total of 275 patients.

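### The SD of 16 for the week-12 change is called conservative without support, and even at SD 16 the two-sided test has 84% power, not 90%

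*Protocol*

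**What the plan says.** The synopsis (Sample Size Determination) states that "250 subjects allow a power of 90% to detect a change of 3 points on the overall convenience domain (from 55 to 58"), and makes this claim "under the conservative hypothesis of a SD=16 for the difference between baseline and week 12". Section 16.5 of the protocol makes the same claim and attaches a reference to the SD of the difference: "under the conservative hypothesis of a SD=16 (9) for the difference between baseline and week 12". SAP section 6 repeats that text.

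The same paragraph gives the single-time-point figure as "Assuming an average value of the overall convenience domain at baseline of 55 (SD=16) (9"). The value and the citation are therefore the same for both quantities. The source is described as one of the "studies reporting the distribution (mean value and standard deviation) of the TSQM-9 in MS patients treated with IFN (9"). Nothing is said about an SD of change.

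The sample size paragraph names neither alpha nor sidedness. Section 16.3.2, repeated in SAP section 10, sets "type I error =0.05 (two-sided test").

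**The concern.** The SD of a paired difference is a different quantity from the SD of one score. It depends on the spread at both visits and on the correlation between them. Here the baseline score rates the patient's previous subcutaneous interferon and the week-12 score rates Peg-IFN, so a high correlation cannot be taken for granted. If 16 was chosen because it is the spread of one score, nothing makes it a cautious choice for the difference.

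Calling it conservative tells an ethics committee or a reader that true power is, if anything, higher than stated. Power is the only justification given for 250 evaluable patients, so the assurance should be one that the documents can back.

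**Working it through.** **Inputs.** n = 250, change = 3 and SD of the difference = 16 (synopsis; section 16.5; SAP 6). Alpha = 0.05 two-sided (section 16.3.2; SAP 10). Entry requires a baseline convenience score below 58 (section 8.1, criterion 5). The correlation r between baseline and week 12 is given nowhere, so every value of r below is an assumption. Powers are from the noncentral t unless marked.

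**1. The plan's own figure.**

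- The standardised effect is 3 × √250 / 16 = 2.965.
- Two-sided 0.05: normal approximation Φ(2.965 − 1.960) = 84.2%; noncentral t 84.0%. The n for 90% is (16 × (1.960 + 1.282) / 3)² = 299 (301 by t).
- One-sided 0.05: Φ(2.965 − 1.645) = 90.7%, with n = 244 for 90%.

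The stated 90% is reproduced only by a one-sided 0.05 test, which is not the test the plan specifies.

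**2. The SD that would give 90%.** With n = 250 and a two-sided test, SD = 3 × √250 / (1.960 + 1.282) = 14.6.

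**3. Is 16 on the safe side?** SD_diff² = s0² + s1² − 2·r·s0·s1, where s0 and s1 are the SDs at baseline and week 12.

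*Equal SDs of 16:* SD_diff = 16 × √(2(1 − r)).

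- r = 0.3: SD 18.9, power 70%.
- r = 0.5: SD 16.0, power 84%.
- r = 0.6: SD 14.3, power 91%.

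*Baseline SD reduced by the entry cut-off.* A mean of 55 with SD 16 cannot occur when all scores lie between 0 and 58, because the SD is then at most √((58 − 55) × 55) = 12.8. As an illustration, take a normal distribution with mean 55 and SD 16 cut at 58. This gives a baseline mean of 44.1 and an SD of about 10.2. With a week-12 SD of 16 and r measured among enrolled patients:

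- r = 0: √(104 + 256) = 19.0, power 70%.
- r = 0.32: √(360 − 104.4) = 16.0, power 84%.
- r = 0.5: √(360 − 163.2) = 14.0, power 92%.

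The cut-off does not limit the week-12 spread. If that SD were 20, SD_diff = 16 would need r = (104 + 400 − 256) / (2 × 10.2 × 20) = 0.61.

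The correlation at which 16 becomes cautious therefore moves from about 0.32 to about 0.61, depending on spreads that the documents do not give.

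**4. Range for n = 250, two-sided 0.05.**

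| SD of difference | Power for 3 points | Change detectable with 90% power |
|---|---|---|
| 14 | 92% | 2.9 |
| 16 | 84% | 3.3 |
| 18 | 75% | 3.7 |
| 20 | 66% | 4.1 |
| 22.6 | 55% | 4.7 |

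**The case against.** **The SD may be properly sourced.** A reader might infer that 16 simply is the cross-sectional SD used a second time. That is plausible but not documented. Section 16.5 and SAP 6 attach reference 9 to the difference SD in its own right. That reference is a prospective study, which could have reported within-patient change, and it cannot be checked here. What can be said is: same value, same citation, no derivation shown.

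**The loss is easily overstated.** With equal SDs of 16 and r = 0, the SD is 22.6 and power falls from 84% to 55%. A reader might take that 29-point drop as the size of the problem. It needs a baseline SD of 16, which the entry cut-off rules out at the planned mean. In the capped illustration, zero correlation costs about 14 points (84% to 70%). A drop near 29 points would then need the further assumption of a week-12 SD of about 20.

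**SD 16 does not mean a correlation of 0.5.** That holds only with equal SDs. In the capped illustration the matching value is about 0.32, and at 0.5 an SD of 16 would indeed be cautious.

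**The statement on switching patients is limited.** Section 5.1 says no data exist "or from patients switching between non-pegylated and pegylated interferon", but it speaks of clinical efficacy and safety studies. It does not bear on how satisfaction scores correlate.

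**A null result would be read from the observed data.** This stands: the observed SD of change and the confidence interval would govern, and the synopsis promises SDs of the changes. In the capped illustration, if the week-12 mean simply returned to 55, selection alone would produce a rise and rejecting zero would be easy. So the harm lies in the stated justification for the sample size more than in how results would be read.

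**Conclusion.** The point holds as an unsupported assurance together with a misstated figure. Accepting the plan's SD of 16, 250 patients and a 3-point change, two-sided power is 84%, about 6 points below the stated 90%. This needs no assumption about correlation, only the two-sided 0.05 test that both documents specify. Separately, nothing in either document shows that 16 errs on the safe side. Power at the planned n runs from 92% at SD 14 to 55% at SD 22.6, and the upper end of that range is an extreme.

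A reader might conclude that the trial is underpowered. The documents do not show that: the SD of the difference could be below 14.6, in which case power would exceed 90%.

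**What to change.** Change the wording in three places: the synopsis, protocol section 16.5 and SAP section 6.

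- Delete the word conservative, or justify it with an SD of change and its source.
- State alpha and sidedness in the sample size paragraph, and replace 90% with 84% at SD 16 under the two-sided 0.05 test.
- Add power for 250 evaluable patients, and the change detectable with 90% power, over SDs of the difference of 14, 16, 18, 20 and 22.6, as in the table above.
- Do not add a statement that SD 16 corresponds to a correlation of 0.5.

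The sample size stays as planned. No patients, visits or procedures are added; the only cost is a less favourable stated power.
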